#### ***7.3.2. Discontinuation of Study Drug(s)***

Patients will be discontinued from the study drugs in the following circumstances:

- progressive disease (PD) as defined by RECIST v1.1
- the investigator decides that the patient should be discontinued from study drugs
- the patient or the patient's designee (eg, parents or legal guardian) requests that the patient be withdrawn from study drugs
- the patient is significantly noncompliant with study procedures and/or treatment
- unacceptable toxicity
- the patient has had 2 dose reductions and experiences an AE that would cause a third dose reduction
- the patient, for any reason, requires treatment with another therapeutic agent that has been demonstrated to be effective for treatment of the study indication, discontinuation from study drugs occurs prior to introduction of the new agent
- enrollment in any other clinical trial involving an IP or enrollment in any other type of medical research judged not to be scientifically or medically compatible with this study

If patients discontinue NSAIs/fulvestrant but continue to receive blinded study drug, this will not be considered as discontinuation of study drug.

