### 10.1. Efficacy Measures

#### 10.1.1. Efficacy Assessments at Baseline and during Study Treatment

Within 28 days of randomization, baseline tumor measurements will be performed on each patient. The method of assessment used at baseline must be used consistently for serial tumor assessment throughout the study. Computed tomography (CT), including spiral CT, scans and magnetic resonance imaging (MRI) are the preferred methods of measurement. In addition, bone scintigraphy will be performed for all patients at baseline (within 28 days of randomization). However, prior bone scintigraphy (obtained as part of routine clinical care) within 45 days before Day 1 of Cycle 1 is also acceptable.

For all patients, imaging studies (CT, including spiral CT, or MRI scan of the chest, abdomen, and pelvis) will be performed locally at baseline and repeated between last 7 days of every second cycle beginning with Cycle 2 and continuing through Cycle 18, in the last 7 days of every third cycle after Cycle 18 (inclusive), and within 14 days of clinical progression per the Study Schedule ([Attachment 1](#)). It is recommended that CT imaging of the abdomen and pelvis be performed with IV contrast, whenever possible. For patients with known hypersensitivity to CT contrast material, a CT scan of the chest without contrast and gadolinium-enhanced MRI of the abdomen and pelvis are encouraged. The CT portion of a positron emission tomography (PET)-CT scan may be used as a method of response assessment if the site can document that the CT is of identical diagnostic quality to a diagnostic CT (with IV and oral contrast). A PET scan alone or as part of a PET-CT may be performed as part of routine clinical care but cannot be used to assess response according to RECIST v1.1.

For only those patients with bone lesions identified by bone scintigraphy at baseline, directed imaging using 1 of the following methods will be performed at baseline: X-ray, CT scan with bone windows, or MRI. Directed imaging using the same method as at the baseline bone lesion assessment should be repeated between last 7 days of every second cycle beginning with Cycle 2 and continuing through Cycle 18, in the last 7 days of every third cycle after Cycle 18 (inclusive), and within 14 days of clinical progression.

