**Table JPBQ.10.1. Other Secondary Efficacy Endpoints**

Endpoint	Definition
Overall Survival (OS)	The time from the date of randomization to the date of death from any cause
Objective Response Rate	The proportion of patients with CR or PR according to RECIST v1.1
Disease Control Rate (DCR)	The proportion of patients with CR, PR, or SD according to RECIST v1.1
Duration of Response (DoR)	The time from the date of first evidence of a CR or PR to the date of objective progression or death from any cause, whichever is earlier
Clinical Benefit Rate (CBR)	The proportion of patients with CR, PR, or SD $\geq$ 6 months according to RECIST v1.1

Abbreviations: CR = complete response; PR = partial response; PS = performance status; RECIST = Response Evaluation Criteria in Solid Tumors; SD = stable disease.

**Overall Survival (OS):** OS duration is measured from the date of randomization of any study drug to the date of death from any cause. For each patient who is not known to have died as of the data-inclusion cutoff date for a particular analysis, OS will be censored for that analysis at the date of last contact prior to the data inclusion cutoff date (contacts considered in the determination of last contact date include AE date, lesion assessment date, visit date, and last known alive date).

**Objective Response Rate:** The objective response rate is the percentage of patients with a best response of CR or PR.

**Duration of Response (DoR):** The DoR time is defined only for responders (patients with a CR or PR). It is measured from the date of first evidence of CR or PR to the date of objective progression or the date of death due to any cause, whichever is earlier. If a responder is not known to have died or have objective progression as of the data inclusion cutoff date scores, duration of response will be censored at the last complete objective progression-free disease assessment date.

**Disease Control Rate (DCR):** The DCR is the percentage of patients with a best response of CR, PR, or SD.

**Clinical Benefit Rate (CBR):** The CBR is the percentage of patients with a best response of CR or PR, or SD for at least 6 months.

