### 10.2.2. Resource Utilization

Investigators will be asked to report the use of concomitant medications (in particular, analgesics, bisphosphonates, and RANK-L targeted agents), blood product transfusions, radiation therapy, surgery, and hospitalization days. Data on neurosurgical blocks will be recorded on the Concomitant Medication and/or Surgery eCRF as appropriate. This information should be collected during the study and at the 30-day follow-up visit.

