### **12.2.11.3. Resource Utilization**

Utilization data will be summarized descriptively by category across arms in a cohort (eg, analgesic use, bisphosphonate use, transfusions, radiation, surgery, and hospitalization days), including a frequency table with tabular statistics. Tests for differences in proportions between treatment groups and between response groups will be performed.

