### **6.7.2.3. Objective Response Rate, Disease control Rate, and Clinical Benefit Rate**

Objective response rate (ORR), disease control rate (DCR), and clinical benefit rate (CBR) are summary measures of best overall response (BOR) as defined by RECIST v1.1. BOR is derived from time point responses. All time point responses observed while on study treatment and during the short term follow up period (but before the initiation of post discontinuation therapy) will be included in the derivation. The one exception includes patients who receive surgery and/or radiotherapy for locally advanced breast cancer. For these patients, only those time point responses occurring prior to surgery/radiotherapy will be included in the derivation.

Each patient's BOR will be categorized as CR, PR, SD, progressive disease (PD), or not evaluable (NE). For patients with bone-only nonmeasurable disease (see Section 6.4.2), BOR will be limited to CR, SD, PD, and NE. Patients with SD will be further classified as SD  $\geq$  6 months or SD < 6 months. Stable disease  $\geq$  6 months includes all patients with a best response of SD and a PFS time of  $\geq$  6 months. A BOR of CR or PR will not require confirmation.

**Objective Response Rate (ORR):** The objective response rate is the percentage of patients with a BOR of CR or PR.

**Disease Control Rate (DCR):** The DCR is the percentage of patients with a BOR of CR, PR, or SD.

**Clinical Benefit Rate (CBR):** The CBR is the percentage of patients with a BOR of CR or PR, or SD for at least 6 months.

For each cohort, the ORR, DCR, and CBR of each treatment arm will be calculated using the ITT population. All rates will be compared between treatment arms within the cohort based on a normal approximation for the difference between the rates.

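### Testing resource use between response groups compares patients with unequal time at risk, and can show a difference when response has no effect on the rate of use

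*Protocol*

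**What the plan says.** Protocol 12.2.11.3 summarises resource use by category ("analgesic use, bisphosphonate use, transfusions, radiation, surgery, and hospitalization days") with a frequency table, and then adds: "Tests for differences in proportions between treatment groups and between response groups will be performed". It does not define the response groups, say how use becomes a proportion, name the test, or give a common window or a time denominator.

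The recording window is set in Protocol 10.2.2: "This information should be collected during the study and at the 30-day follow-up visit". Protocol 12.2.12 limits hospitalizations and transfusions in the same way, to the treatment period and the 30-day follow-up. Protocol 7.3.2 lists "progressive disease (PD) as defined by RECIST v1.1" among the reasons for stopping study drugs, so progression normally closes the window soon afterwards.

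Response is a best response over follow-up. Protocol 10.1.4 states: "The objective response rate is the percentage of patients with a best response of CR or PR". SAP 6.7.2.3 derives it from "All time point responses observed while on study treatment and during the short term follow up period", up to the start of any new therapy, and adds: "A BOR of CR or PR will not require confirmation". Under Protocol 10.1.1, imaging is "repeated between last 7 days of every second cycle beginning with Cycle 2 and continuing through Cycle 18", so the first scheduled chance to respond comes at about 8 weeks.

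Protocol 12.2.11 leaves further detail on health outcomes to the SAP. SAP 6.8 covers only the EORTC QLQ-C30 and the mBPI-sf and does not mention resource use.

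**The concern.** Grouping by best response sorts patients partly by how long they were observed, in two ways. First, a responder must still be progression-free at a scan, whereas a patient who progresses or leaves before the first scan cannot be a responder. Second, response is likely to go with longer PFS, which keeps the window open longer. A proportion without a time denominator then mixes any link between response and resource use with length of observation.

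What is at stake is a supportive statement in the report. A significant result could be read as response raising or lowering the need for care when it reflects only time at risk, and a real reduction could be hidden.

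**Working it through.** **1. The plan's own figures.** Inputs from Protocol 12.1 and 12.2.6: 170 events, hazard ratio 0.626, 2:1 allocation, one-sided 0.025, boundaries p < 0.0082 at 119 events and p < 0.0223 at 170.

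- Fixed design: √(170 × 2/9) × |ln 0.626| = 2.879; 2.879 − 1.960 = 0.919; Φ(0.919) = 82.1%.
- With the two looks, power is 81.41%, against 81.40% stated.
- Median on abemaciclib: 14.4 / 0.626 = 23.0 months. Censoring: 1 − 170/300 = 43%.

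The PFS inputs are reproduced. The documents give no figure for the resource-use test.

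**2. Mechanism.** At a constant use rate λ over a window w, P(any use) = 1 − exp(−λw). Suppose response is unrelated to PFS except that the patient must still be on study, with 33.3% potential response in both arms (the Phase 1 rate in Protocol 5). The simulated mean windows are then 19.7 months in responders and 17.1 in non-responders. At λ = 0.03 per month:

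- responders: 1 − exp(−0.591) = 44.6%
- non-responders: 1 − exp(−0.513) = 40.1%

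Allowing windows to vary between patients gives 42.8% v 37.5%.

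**3. Size with no PFS benefit from response.** Cohort A, 200:100, exponential PFS with medians 23.0 and 14.4 months. Assumptions not in the documents: follow-up uniform from 12 to 30 months; response probabilities of .20, .15, .10, .05 and .05 at successive 8-weekly scans while progression-free (about 39% respond); a constant use rate, unaffected by response, until treatment end plus 1 month; two-proportion z test at two-sided 5%; 4000 trials.

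| Use per month | Any use, responders v non-responders | Rejection, arms pooled |
|---|---|---|
| 1% | 15.7% v 13.1% | 10% |
| 2% | 28.5% v 24.0% | 14% |
| 4% | 47.9% v 40.7% | 23% |

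A repeat run gave 9%, 14% and 24% pooled, 7 to 15% within one arm, and about 5% with a landmark at the third scan (week 24).

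**4. Adding longer PFS in responders.** Other assumptions, arms pooled: 12-month uniform accrual, cutoff at month 33, response at 8/16/24 weeks in 50/30/20% of potential responders, 3000 trials. With 33% potential response in each arm and λ = 0.03:

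| PFS hazard ratio, responders | Mean window (months) | Any use | False finding of more use |
|---|---|---|---|
| 1 | 19.7 v 17.1 | 42.8% v 37.5% | 14% |
| 0.6 | 21.5 v 16.4 | 46.0% v 36.2% | 35% |
| 0.4 | 22.8 v 16.0 | 48.3% v 35.5% | 55% |

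The nominal rate in this one direction is 2.5%. The window gap grows from 19.7 − 17.1 = 2.6 months to 22.8 − 16.0 = 6.8, so in these runs longer PFS can contribute more than the need to reach a scan. Over λ of 0.01 to 0.06 and potential response of 33%/33% or 55%/40%, the false rate was 7 to 43% without the PFS link and 16 to 94% with it.

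**5. Direction by category.**

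- Fixed before randomisation: Protocol 9.6.6 has bone agents started a week or more beforehand. Simulated use was 40.2% v 40.0%, with rejection of 2.6% and 2.0% in the two directions. No bias.
- Linked to progression: under Protocol 9.6.2, radiotherapy generally means leaving treatment. Assuming it occurs in 30% of progressors, use was 17.0% v 18.9% to 11.3% v 22.8%, with false findings of less use in responders in 4.5% to 75% of trials.

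**6. After correction.** With response as a time-dependent state and use per unit of person-time, the rate ratio is 1.00 to 1.01 and total rejection 4 to 6%. With a 6-month landmark and first use counted over the next 6 months, use is 15.5% v 15.2% (15.8% v 14.9% at a responder PFS hazard ratio of 0.4) and rejection is about 5%.

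**The case against.** The strongest reply is that the plan does not say what is being attacked. A reader might infer a yes/no comparison of responders with non-responders, but Protocol 12.2.11.3 states neither the groups nor the proportion. SAP 6.7.2.3 has five best-response categories with not evaluable kept separate, and hospitalization days are a count. This stands as a limit on the claim. It does not remove the problem, because any grouping by best response without a time denominator has unequal windows.

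A reader might also infer that the test will find more use in responders. The documents do not support that. The direction differs by category, and surgery may follow directly from tumour shrinkage (Protocol 9.6.1). In the within-arm runs without a PFS link, 85 to 93% of trials (100 − 15 and 100 − 7) showed nothing. SAP 6.1.1 has analyses done by arm within cohort, so the within-arm range is closer to the plan; pooling adds the PFS difference between arms.

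It can also be said that the two-sided 0.05 rule in Protocol 12.2.1 covers tests of treatment effects, and that proportions which differ through exposure really do differ. That is fair: the error arises when the result is read as a link between response and the rate of use. Without that reading, though, it is hard to see what the test is for.

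Finally, resource use is not a listed objective and has no alpha. The SAP's silence leaves open whether the test will be run, but it does not withdraw the protocol's commitment.

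**Conclusion.** The concern holds in a limited form, and it is minor. The protocol commits to a test between groups that are formed after randomisation and observed for different lengths of time, and nothing in the SAP corrects this.

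On the any-use reading, with 1 to 4% use per month and no PFS benefit from response, a nominal 5% test rejects in about 7 to 15% of trials within one arm and 9 to 24% with arms pooled. Longer PFS in responders raises this. The sizes rest on assumed use rates, response timing and follow-up; the mechanism does not depend on the exact values. The upward bias applies to use that accrues over time, not to every listed category.

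A reader might go on to doubt the trial's main conclusion. There is no ground for that: the primary PFS test uses randomised groups and is not affected.

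**What to change.** End the last sentence of Protocol 12.2.11.3 at the comparison of treatment groups, removing the extension to response groups. This costs one phrase and loses no stated objective.

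If the question is wanted, specify one of the following in the SAP, within each cohort, stratified by arm and labelled exploratory:

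- Landmark: group patients still in follow-up by their response up to a fixed scan (for example Cycle 6), and count only later use, over a common window or per patient-month.
- Time-dependent response: let a patient move into the responder state at first response, and compare rates per patient-month.

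Either needs a small program. The landmark version drops patients who left before the landmark, so it speaks only for those who reached it.

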### **12.2.12. Safety Analyses**

All safety summaries and analyses will be based upon the Safety Population as defined in Section [12.2.1](#).

Overall exposure to study drug, the numbers of patients completing each cycle, and the dose intensity will be summarized using descriptive statistics. The number of patients with any dose adjustment will be presented for the entire treatment period as well as for each cycle. The number of patients with dose reductions, delays, or omissions will also be summarized, as will the reasons for dose adjustments.

Adverse events will be reported using MedDRA. Investigators will report a verbatim AE term and a CTCAE v4.0 term and severity for all AEs. For analysis purposes, the following process will be used:

- The CTCAE v4.0 term reported by the investigator will be mapped to the MedDRA Preferred Term (PT) and SOC using the corresponding MedDRA Lower Level Term (LLT), unless the reported CTCAE term is ‘Other – specify.’
- If the reported CTCAE term is ‘Other – specify,’ the MedDRA LLT, PT, and SOC centrally mapped from the verbatim AE term will be used.
- All listings and summaries will use the PT resulting from this process.

Preexisting conditions are defined as AEs that begin prior to the first dose of study drug.

A TEAE is defined as an event that first occurred or worsened in severity after baseline. Comparisons of preexisting conditions to on-treatment events at the LLT level will be used in the treatment-emergent computation.

The following summaries will be produced by PT within SOC: preexisting conditions, SAEs, TEAEs, drug-related TEAEs, and procedure-related TEAEs.

The following summaries will be produced by PT within SOC and maximum CTCAE grade: laboratory-based TEAEs, nonlaboratory-based TEAEs, drug-related laboratory-based TEAEs, and drug-related nonlaboratory-based TEAEs.

Reasons for death will be summarized separately for on-therapy and within 30 days of treatment discontinuation.

Hospitalizations and transfusions during the study treatment period or during the 30-day short-term follow-up period will be summarized by treatment group.

### **12.2.13. Subgroup Analyses**

Subgroup analyses of PFS will be performed for potential prognostic subgroup variables within each cohort, including:

- All baseline stratification factors
- NSAI received for Cohort A while on study (letrozole vs. anastrozole)
- Study entry disease status (de novo metastatic vs. recurrent metastatic vs. locoregionally recurrent)
- Measurable disease at baseline (yes vs. no)
- Number of organs involved (1 vs. 2 vs. 3+)
- Age (<65 years vs. ≥65 years)
- Country (China vs. Other)
- Race (Asian vs. Other)
- PgR status (positive vs. negative)
- Baseline ECOG PS (0 vs. 1)

If a level of a factor consists of fewer than 5% of total randomized patients in the study, analysis within that level may be omitted. The final list of subgroup analyses will be provided in the SAP.

Analyses will be done within subgroups and, separately, across subgroups with a test of interactions of subgroups with treatment performed.

Other subgroup analyses may be performed as deemed appropriate.

### **12.2.14. Interim Analysis and Other Planned Analyses**

An interim analysis on Cohort A will be conducted by the DMC after approximately 119 PFS events have been observed. The interim analysis will be conducted to provide early efficacy information and could potentially result in early communication with regulatory agencies. The O'Brien Fleming alpha spending function (Lan and DeMets 1983) will be used to preserve the overall type I error. If the analysis of PFS is significant using the cutoff described in Section 12.2.6, the DMC will be instructed to engage the SMD, who may subsequently convene an IRC to propose actions based upon the DMC's recommendation. All patients will continue

follow-up for PFS until study completion, and will remain blinded for the duration of the study unless emergency unblinding (Section 9.5.2) are met. If Cohort A show early efficacy at interim, the sponsor may consider early stop, unblinding and crossover for this cohort; however, regulatory agencies will be consulted before any action is taken.

The unblinded analysis, including review of the efficacy along with the safety data, will be conducted by the DMC. Only the DMC is authorized to evaluate unblinded interim efficacy and safety analyses. Study sites will receive information about interim results ONLY if they need to know for the safety of their patients.

If statistical significance is not declared at the interim, a final analysis of Cohort A will be conducted with about 170 PFS events.

The interim analysis of Cohort B is triggered only if statistical significance is declared at the Cohort A interim analysis. No DMC is required for the analysis of Cohort B. The analysis will provide both safety and efficacy information of Cohort B and could potentially result in early communication with regulatory agencies, including consultation of potential decisions regarding early stop, unblinding and crossover before any action is taken.

In the case of early stop and crossover for Cohort A or Cohort B after the interim analysis, Lilly will notify investigators when the crossover begins.

If patients in Cohort A continue being followed for PFS until final analysis, the final analysis of Cohort B will be conducted at the same time of Cohort A final analysis. If Cohort A stops early at interim due to efficacy, the final analysis of Cohort B may be conducted after approximately 105 PFS events have been observed in Cohort B.

Unblinding details are specified in the unblinding plan section of the SAP.

## 13. Informed Consent, Ethical Review, and Regulatory Considerations

### 13.1. Informed Consent

The investigator is responsible for ensuring that the patient understands the potential risks and benefits of participating in the study, including answering any questions the patient may have throughout the study and sharing in a timely manner any new information that may be relevant to the patient's willingness to continue his or her participation in the trial.

The ICF will be used to explain the potential risks and benefits of study participation to the patient in simple terms before the patient is entered into the study, and to document that the patient is satisfied with his or her understanding of the risks and benefits of participating in the study and desires to participate in the study.

The investigator is responsible for ensuring that informed consent is given by each patient or, where permitted by local law or regulation, by the patient's legal representative. This includes obtaining the appropriate signatures and dates on the ICF prior to the performance of any protocol procedures and prior to the administration of study drug.

As used in this protocol, the term "informed consent" includes all consent and assent given by patients or their legal representatives.

